Aim 1. To collect samples of breath and sweat during normoglycemia (both in the early and late post-prandial periods) and hypoglycemia in 20 adult (≥ 18 years of age) subjects with type 1 diabetes.

Breath and sweat samples will be collected at intervals throughout the visit, with increased frequency during hypoglycemia. Collaborators with the MITRE Corporation will perform analyses on these samples to identify any relationships between volatile organic compounds in breath and sweat and hypoglycemia.

III. Subject Selection

III. a. Inclusion Criteria

- Informed consent by the subject documented prior to any study procedures
- Age ≥ 18 years
- Have had clinical type 1 diabetes for at least one year
- Willing and able to avoid deodorant, scented lotions, and scented laundry detergent on your clothes on the day of the visit

No subjects will be excluded on the basis of gender or race. The requirement that subjects manage their diabetes using subcutaneous insulin infusion pump therapy is imposed because multiple daily injection therapy involves the use of long-acting basal insulin that would require an extended washout period.

III. b. Exclusion Criteria

- Unable to provide informed consent (e.g. impaired cognition or judgment)
- Unable to safely comply with study procedures and reporting requirements (e.g. impaired memory or unable to speak and read English)
- Current participation in another diabetes-related clinical trial that, in the judgment of the principal investigator, will compromise the results of this study or the safety of the subject
- Pregnancy (positive urine HCG), breast feeding, plan to become pregnant in the immediate future, or sexually active without use of contraception
 - Subjects must use acceptable contraception for the two weeks prior to the study, throughout the study and for the two weeks following the study.
 - Acceptable contraception methods include:
 - Oral contraceptive pill (OCP)
 - Intrauterine Device (IUD, hormonal or copper)
 - Male condoms
 - Female condoms
 - Diaphragm or cervical cap with spermicide
 - Contraceptive patch (such as OrthoEvra)
 - Contraceptive implant (such as Implanon, Nexplanon)
 - Vaginal ring (such as NuvaRing)
 - Progestin shot (such as Depo-Provera)
 - Male partner with a vasectomy proven to be effective by semen analysis

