Yellow Springs Instrument (YSI) 2300 STAT PLUS: The YSI model 2300 STAT PLUS Glucose and Lactate Analyzer is a laboratory instrument that is intended for use in clinical care. It provides quick measurements of glucose in whole blood, plasma or serum and will be used to measure plasma glucose during the study visit. This device will be stored at the Diabetes Research Center when not in use, and study staff will follow proper maintenance and quality assurance procedures.

V. d. Experimental Procedures and Data Collection

V. d. i. Screening Visit

- All subjects will have a screening visit to confirm eligibility. Informed consent will be obtained and documented with a signed informed consent document before any trial-related procedures are conducted.
- The subject will be interviewed and the case report form will be completed by study staff to establish whether the subject is eligible to continue with the screening.
- A urine pregnancy test will be performed in female volunteers. If the test is positive the volunteer will be informed of the result and the visit will be ended.
- Height, weight and blood pressure will be measured.
- If the volunteer is not excluded based on historical criteria, blood pressure, or urine pregnancy test, blood will be drawn for hemoglobin and hemoglobin A1c.
- Questionnaires will be administered to assess impaired awareness of hypoglycemia.
- Once all of the laboratory results have been returned, a study MD or NP will review the case report form
 to determine subject eligibility. If subjects are not eligible to continue in the study the results of abnormal
 tests will be reported to the subjects and to a health care provider of their choosing.
- Subjects who have been screened and are eligible can participate without having to be re-screened for a
 period of one year. The study staff should verbally confirm that there have been no health events that

would make them ineligible if the interval between screening and participation is longer than 3 months.

V. d. ii. Visit Procedures

- Subjects will arrive to the visit having fasted since 12:00 AM the night before. Treatment with simple carbohydrates of up to 30 grams for a low blood sugar is allowed. Subjects are also allowed to treat any hyperglycemia as they normally would. If the patient is not fasted, the visit will be rescheduled.

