- A urine pregnancy test will be performed in female volunteers upon arrival to the study visit. If the test is positive the volunteer will be informed of the result and the visit will be ended. The date of the last menstrual period will also be documented, along with usual cycle length, for female subjects.
- A plasma glucose will be checked via fingerstick using the Contour Next One meter upon arrival. If PG is ≥250 mg/dL the visit will be rescheduled. If PG is <50 mg/dL, the patient will be treated with simple carbohydrates according to the 15/15 rule (15 grams of ≥carbohydrates, repeated in 15 minutes if necessary). If PG is <70 mg/dL and the patient has symptoms of hypoglycemia they may elect to be treated with simple carbohydrates according to the 15/15 rule (15 grams of ≥carbohydrates, repeated in 15 minutes if necessary).
- We will ask subjects to avoid certain skin care products that will interfere with sweat sample collection on the day of the visit.
- We will ask subjects to bring a breakfast of their choosing to the visit.
- A 20 gauge or smaller peripheral I.V. will be placed.
- Subjects will calculate their insulin dose based on their insulin to carbohydrate ratio for the breakfast meal they brought to the visit. A correction bolus of insulin will also be added to the meal correction dose.
 - The dose of insulin will be calculated using their own correction factor, correcting them down to a target PG of 40 mg/dl using their current PG.
 - O Both doses of insulin will be combined into one syringe and injected into the subcutaneous tissue.
- Subjects will then eat breakfast.
- BG measurements using the YSI will be obtained per the following protocol:
 - o If PG is ≥ 120 mg/dl, BG measurements will be obtained off the IV line every 30 minutes.
 - o If PG is 100-119 mg/dl, BG measurements will be obtained off the IV line every 20 minutes.
 - o If PG is 80-99 mg/dl, BG measurements will be obtained off the IV line every 10 minutes.
 - o If PG is < 80 mg/dl, BG measurements will be obtained off the IV line every 5 minutes.
 - Study staff will collect samples of sweat from the subject's underarm and will ask subjects to exhale into a breath collection device throughout the visit, with increased frequency during any episodes of hypoglycemia. These samples will be collected, de-identified and shipped out to collaborators at the MITRE Corporation for analysis of the relationship between volatile organic compounds in breath and sweat and hypoglycemia.

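### Skin products are barred only on the visit day and their use is not recorded, so deodorant from the evening before may be mixed into the underarm sweat samples

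*Combined protocol and SAP*

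**What the plan says.** The restriction appears in two places in the combined protocol and SAP. Under III.a (Inclusion Criteria) a subject must be "Willing and able to avoid deodorant, scented lotions, and scented laundry detergent on your clothes on the day of the visit". Under V.d.ii (Visit Procedures) the wording is a request: "We will ask subjects to avoid certain skin care products that will interfere with sweat sample collection on the day of the visit". Both limit it to the visit day, and the second states that such products interfere with the sweat sample.

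On site and timing, V.d.ii says "Study staff will collect samples of sweat from the subject's underarm", "Subjects will arrive to the visit having fasted since 12:00 AM the night before" and "We will ask subjects to bring a breakfast of their choosing to the visit". No clock time is given for arrival or for the first sweat sample.

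Other pre-visit conditions are handled more firmly. For fasting: "If the patient is not fasted, the visit will be rescheduled". On arrival, "A urine pregnancy test will be performed in female volunteers upon arrival to the study visit" and "A plasma glucose will be checked via fingerstick using the Contour Next One meter upon arrival". The data lists in VI.a have no item for skin products.

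VI.b makes compounds in breath and sweat that correlate with hypoglycemia the primary endpoint. VI.c expects at least 12 visits with hypoglycemia. Each should give at least one sample set during hypoglycemia and at least four during normoglycemia, taken on both sides of the episode in the same person on the same day.

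**The concern.** The plan accepts that skin products can spoil the sweat sample, but the rule reaches back only to midnight. If subjects arrive in the morning, product applied late the evening before breaks no rule and may still be on the skin at the sampling site. The sweat sample would then be a mixture of the subject's own volatiles and those of the product.

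This matters because the endpoint is an open search across compounds and because glucose state is ordered in time within the visit. Residue that changes during the visit can change alongside glucose. Since nothing records use, an analyst who found a fragrance-like compound among the sweat candidates could not check which subjects had used product, nor repeat the analysis without them. That gap cannot be repaired after the samples are taken. I.c removes exercise from this study to avoid spurious correlations, and the same reasoning applies here.

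**Working it through.** The plan gives no figure on this point to reproduce. The check sets the passages side by side and adds two small illustrations on assumed values.

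**1. What the rule guarantees.** Product-free hours at arrival = arrival time minus 12:00 AM. Arrival time is not stated; a morning start is inferred from the fast and the breakfast.
- Assumed arrival 7:00 to 10:00 AM: 7 to 10 hours.
- Assumed arrival 8:00 AM: 8 hours.
- Longest visit, taking injection at 8:00 AM: 3 h to the second bolus + 2 h further observation = 13 hours after midnight. If the threshold is reached only then, the 1 h that V.d.ii requires at or above 70 mg/dl gives at least 14.

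These are minimum intervals for a subject who applied product just before midnight.

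**2. What is checked.** The steps on arrival in V.d.ii cover fasting status, a pregnancy test and last menstrual period in female subjects, and a fingerstick glucose. None asks about product use, cleans the underarm or takes a blank swab.

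**3. Could residue still be present and changing?** Assume first-order loss with half-life h, product applied 12 h before the first sample, and hypoglycemia 3 h after that sample.
- Fraction left at the first sample = 2^(−12/h).
- Further fall by hypoglycemia = 1 − 2^(−3/h).

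| h (assumed) | Left at first sample | Fall over next 3 h |
|---|---|---|
| 2 h | 2% | 65% |
| 4 h | 13% | 41% |
| 8 h | 35% | 23% |
| 12 h | 50% | 16% |

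**4. How much do the bracketing samples correct?** Add one normoglycemic sample 1 h after the hypoglycemic one (assumed). Scale the first sample to 1, so that during = 2^(−3/h) and after = 2^(−4/h). Two comparisons are possible.
- Against the plain mean of before and after, (1 + after)/2. For h = 4 h: 0.595 against 0.750, a difference of −21%. For h = 8 h: 0.771 against 0.854, or −10%.
- Against a straight line in time between them, 1 − 0.75 × (1 − after). For h = 4 h: 0.595 against 0.625, or −5%. For h = 8 h: 0.771 against 0.780, or −1%.

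Constant residue cancels in both. A smooth decline is largely corrected if the analysis uses sampling time, and less so if it does not. The plan states no model, so which applies is unknown. Neither comparison corrects a change tied to the episode itself, such as release with sweating, or depletion from the more frequent sampling that Aim 1 and V.d.ii schedule during hypoglycemia.

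**The case against.** The strongest reply is the paired design. Constant residue cancels within subject. Residue that only declines gives before > during > after, which is a time trend and not a hypoglycemia pattern. This stands, and it removes much of the harm. What is left is non-linear or episode-linked change. The documents neither show that this happens nor rule it out.

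A reader might infer that residue would replace the subject's own volatiles. The text supports only that it may be mixed with them. A reader might also infer that a few users among about 12 hypoglycemic visits would create or hide a marker. That is not shown: they would probably need to share a compound moving in the same direction, and there are no data on use, persistence or sweat output. A count such as 3 of 12 (25%) would be an assumption only. The preliminary breath work identified the compounds present; if sweat is handled likewise, a product compound might be recognised by its identity.

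The absence of a check is read from silence. Consent pages are not in the text reviewed, and the case report forms and sweat-handling instructions are not shown; any of these might say more. IX.b also allows removal for not complying with study procedures. That could reach use on the visit day, but not compliant use the evening before. Finally, 24 hours has no source in the documents and is offered only as an example of an earlier start.

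**Conclusion.** The point holds as a cheap improvement. The restriction starts on the day of what appears to be a morning visit, evening-before deodorant is compliant, and no listed step or data field records it. Residue may therefore be mixed into the underarm sweat samples without any later means of telling where.

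The size of the effect cannot be determined from the documents. The 7 to 10 product-free hours rest on an assumed arrival time, and the residue fractions of 2% to 50% rest on assumed half-lives and application time. The same-day samples on both sides of hypoglycemia limit the harm to residue that changes non-linearly or is released with sweating during the episode.

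The documents do not support reading this as a fault in the whole primary endpoint: nothing in the plan links these products to the breath samples. Nor do they support mandatory rescheduling, or dropping sweat sets from the main analysis. With about 12 hypoglycemic visits expected, that would give up scarce data for an unquantified risk.

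**What to change.** 1. In III.a and V.d.ii, use one list of products and start the restriction before the visit day. An example is no deodorant, antiperspirant or scented lotion for 24 hours before arrival, with one underarm wash with plain unscented soap in that period.
2. Add an arrival question to V.d.ii on product and time of last use, and a matching field in VI.a and the case report form.
3. In VI.b, prespecify a sensitivity analysis that repeats the sweat VOC analysis without subjects who used product inside the window. Keep their sweat sets in the main analysis and their breath data throughout.

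The cost is a wording change, one question, one form field and minor inconvenience to subjects. The sensitivity analysis will be small (if 3 of 12 had used product, 9 would remain), so it should be read for consistency of direction and size and not for significance.

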- Abnormal EKG consistent with coronary artery disease or increased risk of malignant arrhythmia including, but not limited to, evidence of active ischemia, prior myocardial infarction, proximal LAD critical stenosis (Wellen's sign), prolonged QT interval (> 440 ms). Non-specific ST segment and T wave

changes are not grounds for exclusion in the absence of symptoms or history of heart disease. A reassuring evaluation by a cardiologist after an abnormal EKG finding may allow participation.

- History of hypoglycemic seizures (grand mal) or coma in the last year
- History of poor venous access or inadequate venous access as determined by trial nurse or physician at time of screening
- Hemoglobin < 12 g/dl for men, < 11 g/dl for women
- Any factors that, in the opinion of the principal investigator would interfere with the safe completion of the study

III. c. Source of Subjects

Volunteers who fit the selection criteria will be considered as candidates for this study. We will contact individuals who have previously inquired about participation in our studies and have asked us to have their contact information kept on file. In addition, advertisements for the study may be posted at the MGH Diabetes Center and other places, and may be distributed in the weekly broadcast email of research studies seeking volunteers. A letter may be sent to adult endocrinologists in the Boston metropolitan as well as selected nearby endocrinologists informing them of the study and asking them to refer any eligible patients who might be interested. We will post information about the trial along with contact information on our website www.bionicpancreas.org and on www.clinicaltrials.gov.

IV. Subject Enrollment

IV. a. Number of Subjects

It is expected that we will have 12 subjects complete the study and reach a plasma glucose of <60 mg/dl for 3 measurements at 5 minute intervals or a plasma glucose of <50 mg/dl for 1 measurement. We expect that the experiments and analysis can be accomplished over a period of 6-12 months. Up to 24 subjects will be enrolled. The upper bound is based on the expectation that some volunteers will be excluded after the screening visit, the possibility that some experiments may have to be discontinued before completion, and the likelihood that some subjects will not reach the hypoglycemic threshold during the experiment.

IV. b. Enrollment and Consent Procedures

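### Apart from the pregnancy test, no re-check of eligibility is scheduled before the insulin injection when 3 months or less have passed since screening

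*Combined protocol and SAP*

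**What the plan says.** Section V.d.i (Screening Visit) sets two rules for the time between screening and the study visit. The first keeps an eligible participant's screening valid for one year, with no repeat needed in that time. The second is a conditional check, in which staff are to establish by asking that nothing has happened to the participant's health that "would make them ineligible if the interval between screening and participation is longer than 3 months". No repeat test is named as part of that check.

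Section V.d.ii (Visit Procedures) lists the steps on the day. Three of them can stop or postpone the visit whatever the interval since screening:

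- Fasting: "If the patient is not fasted, the visit will be rescheduled".
- Pregnancy: "A urine pregnancy test will be performed in female volunteers upon arrival to the study visit". A positive result ends the visit.
- Arrival glucose: "If PG is ≥250 mg/dL the visit will be rescheduled".

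The IV line, the insulin calculation (correcting to a target of 40 mg/dl) and the injection follow.

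Section III.b (Exclusion Criteria) includes "History of hypoglycemic seizures (grand mal) or coma in the last year", EKG findings, hemoglobin limits and an open-ended exclusion at the principal investigator's discretion.

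**The concern.** Several III.b exclusions can become true after screening. The seizure or coma criterion looks back over a year, so it is naturally read as applying up to the day of exposure. Cardiac status and hemoglobin can also change. The protocol accepts that eligibility can lapse between the two visits, because it repeats the pregnancy test on the day and adds a verbal check after 3 months. It gives no reason why other health events need no question when the gap is shorter.

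The visit induces hypoglycemia on purpose. A recent hypoglycemic seizure or coma is an exclusion that bears directly on that exposure, and at shorter gaps nothing in the visit steps is designed to reveal one.

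**Working it through.** The plan states no figure to reproduce. The check is mainly a comparison of sections, followed by a rough size.

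**Which exclusions have a scheduled check before insulin?**

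| III.b item | Gap of 3 months or less | Gap over 3 months, up to 1 year |
|---|---|---|
| Pregnancy | Urine test on arrival | Urine test on arrival |
| Hypoglycemic seizure or coma | None scheduled | Verbal confirmation |
| Cardiac event or new EKG finding | None scheduled | Verbal confirmation; no repeat EKG |
| Fall in hemoglobin | None scheduled | Verbal confirmation; no repeat blood test |
| Other new health event | None scheduled | Verbal confirmation |

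The fasting and arrival-glucose steps are conditions for holding the visit that day. They are not III.b criteria, so they do not fill the empty cells.

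**Does VI.a.1 fill them?** The list of data collected before the experiment starts includes medical history, medications, hemoglobin, and EKG where applicable. It gives no timing and largely repeats the screening list in V.a. If it meant a fresh history at every study visit, the 3-month condition in V.d.i would have no purpose. It therefore does not establish a visit-day check, although the two sections should be aligned.

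**Illustration.** A participant is screened, has a hypoglycemic seizure at week 8 and attends at week 10. The person meets a III.b exclusion. The gap is under 3 months, so no question is scheduled that would bring the seizure to light.

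**Size.** Inputs:

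- Participants: 24, the upper limit on enrollment in IV.a.
- Length of the unchecked window: at most 3 months = 0.25 year, from V.d.i.
- Yearly rate of a new excluding event: not in the documents; assumed to be 1% to 5%.

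Expected number newly ineligible = participants × mean gap in years × yearly rate.

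- Every gap a full 3 months: 24 × 0.25 × 0.01 = 0.06, and 24 × 0.25 × 0.05 = 0.30.
- Gaps spread evenly over 0 to 3 months (mean 0.125 year, also an assumption): 24 × 0.125 × 0.01 = 0.03, and 24 × 0.125 × 0.05 = 0.15.

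These figures count newly ineligible participants, not harms. They also assume that no event is volunteered or noticed. IV.a expects some of the 24 to be excluded after the screening visit, which would lower the numbers further.

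**The case against.** The strongest reply is that V.d.i only says when staff must ask. It does not suspend III.b. The discretionary exclusion in III.b carries no time limit, and IX.b allows removal for concurrent illness at any interval. Every participant has been interviewed and tested at screening, and a study MD or NP has reviewed the case report form. During the visit, glucose is measured every 5 minutes below 80 mg/dl, carbohydrate treatment is required at stated thresholds, and section VII promises direct supervision by an NP, RN or MD throughout. On this view, a graded re-check is a legitimate design choice that no other section contradicts.

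Much of this stands, and it rules out three stronger readings that a reader might infer:

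- **That eligibility is never re-confirmed within 3 months.** The pregnancy test is repeated at every study visit, and a positive result ends the visit.
- **That the protocol has ineligible people dosed.** No section directs insulin for a person known to be ineligible, and staff who know of an event can exclude or remove that person.
- **That the exclusions do not work for anyone attending within 3 months.** They were applied at screening. Only a new event in the window can escape a scheduled question.

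What the reply does not answer is detection. Discretion and removal depend on staff knowing of the event, and at 3 months or less no step asks about one. Supervision manages hypoglycemia once it has been induced, whereas the exclusions are there to keep certain people from being exposed at all.

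**Conclusion.** There is a real but small gap in detection. When 3 months or less have passed since screening, a new III.b exclusion other than pregnancy has no scheduled point of discovery before insulin. The participant could then have hypoglycemia induced, unless the event is volunteered or otherwise known.

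That rests on the text of V.d.i and V.d.ii alone. The size does not: 0.06 to 0.30 expected participants is a ceiling for the assumed rates of 1% to 5% per year, with all 24 participants at the maximum gap, and 0.03 to 0.15 applies if gaps are evenly spread. The documents support neither a firmer number nor a claim about how many would be harmed.

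The severity is minor. The change is worth making because it costs very little and the question precedes deliberate hypoglycemia. It does not affect the sample size or the analysis.

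**What to change.** - In V.d.i, remove the 3-month condition. Staff would confirm verbally and document, at every study visit and before insulin, that no health event since screening makes the participant ineligible under III.b.
- In V.d.ii, add this confirmation to the arrival steps, ahead of the injection.
- In VI.a.1, state which items are collected at screening and which are confirmed on the visit day, so that the three sections agree.
- Leave the one-year validity of the screening tests as it is.

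The cost is a sentence in V.d.i with matching edits in the other two sections, one entry on the visit form, and about a minute per visit. No extra test is needed. The limit of the change is that a verbal question finds only events the participant knows about. A silent fall in hemoglobin or change in EKG would still be missed, as it is now at any interval.

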- Subjects will be required to treat with 15g of rapid acting carbohydrates:
 - If PG <50 mg/dl for two consecutive measurements
 - o If PG is <40 mg/dl for one measurement
- Subjects will be given the option to treat with 15g of rapid acting carbohydrates:
 - O If PG is <60 for three consecutive measurements
 - If PG is <50 mg/dl for one measurement
 - O Repeat treatments will be given at 15 minute intervals if hypoglycemia continues
 - If the YSI fails, the Contour Next One meter will be used for glucose measurements.
- If the subject reaches a hypoglycemia threshold they will be treated with carbohydrates as above and
 they will be discharged from the DRC when they have maintained a PG ≥ 70 mg/dl for 1 hour. They will
 be allowed to treat with further oral carbohydrates at their discretion during this time to maintain their
 blood glucose.

- If the subject does not reach the hypoglycemia threshold 3 hours after the insulin injection, another correction bolus will be given via syringe per the same protocol:
 - The dose of insulin will be calculated using their own correction factor, correcting them down to a target PG of 40 mg/dl using their current PG.
 - o If the subject does not reach the hypoglycemia threshold after an additional two hours, they will be permitted to eat breakfast and be discharged.
- If the subject reaches a hypoglycemia threshold a hypoglycemia threshold they will be treated with carbohydrates as above and they will be discharged from the DRC when they have maintained a PG ≥ 70 mg/dl for 1 hour. They will be allowed to treat with further oral carbohydrates at their discretion during this time to maintain their blood glucose.

VI. Bio Statistical Analysis

VI. a. Data Collected

VI. a. 1. Prior to start of experiment:

- Age
- Sex
- Race and ethnicity
- Date of last menstrual period in female subjects
- Date of diabetes diagnosis
- Medical, surgical, and social history, allergies, and review of systems relevant to inclusion and exclusion criteria
- Medications (prescription and non-prescription) and date of last change in medication regimen
- Insulin regimen
- Average total daily dose of insulin in the last 30 days as available
- Height and weight
- Blood pressure
- EKG if applicable
- Hemoglobin A1c
- Hemoglobin
- Urine HCG (pre-menopausal females)

VI. a. 2. During the experiment:

- Plasma glucose
- Breath and sweat VOCs
- Carbohydrate intake

VI. b. Study Endpoints

VI. b. 1. Primary endpoint analyses

VOC outcomes

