- Identification of volatile and organic compound or compounds in breath and sweat that correlate(s) with hypoglycemia
- Identification of volatile organic compounds in breath and sweat that correlate with normoglycemia and/or hyperglycemia

VI. c. Power Analysis

Power Calculation for Aim 1

No formal power analysis has been completed for the determination of a relationship between VOCs and hypoglycemia. We expect to capture breath and sweat in at least 12 visits during which hypoglycemia (BG < 60 mg/dl) occurs. During visits in which hypoglycemia occurs, we will capture at least one set, and likely 2 or more

sets, of samples of breath and sweat during hypoglycemia, and at least 4 during normoglycemia in the same participants on the same day. This is anticipated to provide samples from 12 hypoglycemic episodes and paired samples during normoglycemia (both before and after hypoglycemia) from the same participants. If there is a robust correlation between a VOC marker and hypoglycemia, this should provide sufficient power to identify VOC markers of hypoglycemia.

VII. Risks and Discomforts

The protocol is designed to cause mild hypoglycemia. Given frequent PG monitoring, protocols for treating hypoglycemia, and direct supervision by an NP, RN, or MD at all times, the risk of a hypoglycemic episode leading to significant harm to volunteers is expected to be very low, but the symptoms of hypoglycemia may be unpleasant. All study NPs, RNs, and MDs have experience in managing hypoglycemic episodes.

Subjects may experience discomfort with insertion of the peripheral intravenous line and the injection of insulin into the subcutaneous tissues.

There is a risk of risk of dizziness or lightheadedness from blood loss. However, typical blood loss will be limited to no more than 170 ml. Exclusion of subjects with anemia will help mitigate this risk.

VIII. Potential Benefits

The data derived from this study will allow us to evaluate whether there is a relationship between volatile organic compounds in the breath and sweat and hypoglycemia. This information could be useful in developing noninvasive technologies to identify impending and actual hypoglycemia.

Subjects will be financially compensated for participating in the study.

IX. Data and Safety Monitoring IX. a. Monitoring of Source Data

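### At 3 hours a subject already at 50-59 mg/dl with only one or two consecutive readings below 60 must get the second bolus, although the next one or two 5-minute readings may meet the threshold without it

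*Combined protocol and SAP*

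**What the plan says.** The second-bolus rule is in V.d.ii (Visit Procedures): "If the subject does not reach the hypoglycemia threshold 3 hours after the insulin injection, another correction bolus will be given via syringe". The dose uses the subject's own correction factor, "correcting them down to a target PG of 40 mg/dl using their current PG". The rule names no minimum glucose and no circumstance in which staff should wait.

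IV.a (Number of Subjects) gives the fullest statement of the threshold. It expects 12 subjects to complete and "reach a plasma glucose of <60 mg/dl for 3 measurements at 5 minute intervals or a plasma glucose of <50 mg/dl for 1 measurement". The optional-carbohydrate tier in V.d.ii has the same two limbs: "If PG is <60 for three consecutive measurements" and "If PG is <50 mg/dl for one measurement". The required tier is stricter: below 50 mg/dl twice running, or below 40 once.

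On sampling, V.d.ii says: "If PG is < 80 mg/dl, BG measurements will be obtained off the IV line every 5 minutes". After the second bolus: "If the subject does not reach the hypoglycemia threshold after an additional two hours, they will be permitted to eat breakfast and be discharged". VI.c (Power Analysis) describes hypoglycemia by a single value, expecting samples from "at least 12 visits during which hypoglycemia (BG < 60 mg/dl) occurs".

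**The concern.** The second bolus exists to bring on hypoglycemia in a subject who has not got there. At the 3-hour mark the rule looks only at whether the threshold has been met. It does not ask whether the subject is part-way through meeting it. A subject whose latest value is 50-59 mg/dl, with one or two consecutive readings below 60, is therefore given more insulin aimed at 40 mg/dl, when one or two further readings might have met the threshold and opened the carbohydrate option.

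At stake is an insulin dose that may be unnecessary in a subject who is already low. The count of 12 is not threatened, because a subject who meets the threshold during a short wait still counts under IV.a. No endpoint or analysis is touched.

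**Working it through.** The plan gives no figure on this point to reproduce. The check applies its rules to every possible short run of readings.

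**Inputs.** Threshold: IV.a, with the three readings taken as consecutive, as in the optional tier of V.d.ii. Sampling: every 5 minutes below 80 mg/dl (V.d.ii). Bolus time: 180 minutes; further observation: 120 minutes (V.d.ii). Dose: (PG - 40)/CF units (V.d.ii). The documents give no correction factors, so CF = 20 to 100 mg/dl per unit is an assumption.

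**Step 1: who is exposed.** Code each reading as L (below 50), M (50-59) or H (60 or above), at 170, 175 and 180 minutes.
- All patterns: 3 × 3 × 3 = 27.
- Threshold not met: no L and not M-M-M, so 2 × 2 × 2 - 1 = 7.
- Of those 7, ending in M: H-H-M and M-H-M (one consecutive reading below 60) and H-M-M (two). These 3 require a bolus at PG 50-59.

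Examples: 62, 61, 49 has met the threshold, so no bolus. 58, 57, 56 has met it, so no bolus. 62, 58, 56 has not, so bolus. 64, 61, 58 has not, so bolus.

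**Step 2: what a short wait would show.**

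| Consecutive readings below 60 at 180 min | Next readings | Outcome |
|---|---|---|
| two | L at 185 | met, no bolus |
| two | M at 185 | met, no bolus |
| two | H at 185 | bolus at 185 |
| one | L at 185 | met, no bolus |
| one | H at 185 | bolus at 185 |
| one | M at 185, L at 190 | met, no bolus |
| one | M at 185, M at 190 | met, no bolus |
| one | M at 185, H at 190 | bolus at 190 |

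There are 8 paths: 5 meet the threshold with no bolus, 3 give the bolus, and none is open after 190 minutes. These are counts of paths, not probabilities. Continuing the examples, 62, 58, 56 then 55 meets the threshold at 185, and 64, 61, 58 then 57, 56 meets it at 190.

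**Step 3: width of the window.** If a steadily falling subject first reads below 60 at time t, the third such reading is due at t + 10. It falls after 180 only if t is later than 170, so the window is 170 < t ≤ 180, or 10 of 180 + 120 = 300 minutes. On the 5-minute schedule t is 175 or 180, and the third reading comes 5 or 10 minutes after a bolus given at 180.

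**Step 4: dose.**

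| PG when dosed (mg/dl) | PG - 40 | Units at CF 20 | Units at CF 100 |
|---|---|---|---|
| 50 | 10 | 0.50 | 0.10 |
| 59 | 19 | 0.95 | 0.19 |
| 60 | 20 | 1.00 | 0.20 |
| 65 | 25 | 1.25 | 0.25 |
| 70 | 30 | 1.50 | 0.30 |

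The bolus at issue is thus 0.10 to 0.95 units. One released after a wait is at least 20/CF, and more if glucose has rebounded above 60.

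**Step 5: clock.** A bolus at 180, 185 or 190 minutes ends the two-hour period at 300, 305 or 310 minutes.

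**The case against.** The strongest reply is that the dose fits the design. VII (Risks and Discomforts) says that mild hypoglycemia is intended, the study needs samples taken during it, and a subject at 55 may rebound, as 3 of the 8 paths do. This stands as far as it goes, but the hold still gives the bolus on exactly those 3 paths. Nor is the second bolus written to prolong hypoglycemia: a subject with 58, 57, 56 at 180 minutes gets none.

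Safeguards also stand: 5-minute readings, required carbohydrate at below 50 twice or below 40 once, and constant supervision by an NP, RN or MD. One is narrower than it looks. Discharge only after an hour at 70 mg/dl or above applies to subjects who reach a threshold; V.d.ii states no glucose level for discharging those who do not.

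Two criticisms of the remedy are fair. It makes a step at 60: a subject at 60 or 61 is dosed at once with 20/CF or 21/CF, though that subject too might soon meet the threshold. And release can mean more insulin than the current rule gives.

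A reader might infer three stronger things, and the documents support none of them.
- That the threshold is undefined. V.d.ii ties reaching a threshold to the carbohydrate tiers just above it. Any required-tier event also meets the optional tier, so together the tiers match IV.a apart from the word consecutive. The single-value description in VI.c concerns expected sample numbers and is a weak rival.
- That insulin is ordered for a subject below 50. One such value meets the threshold, so no bolus is due.
- That this is a serious hazard or harms the analysis. The doses are small, the safeguards are real, and no statistical figure depends on the rule.

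**Conclusion.** The point holds as a minor safety improvement. Followed literally under the IV.a threshold, the 3-hour rule requires insulin for a subject at 50-59 mg/dl who may be one or two readings from meeting the threshold unaided. The dose may be unnecessary; the documents cannot show that it would be.

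For a steadily falling subject the window is about 10 minutes, and up to 24 subjects are enrolled. How many would fall in it is not known from the documents and may be zero.

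The conclusion rests on IV.a being the threshold that V.d.ii means, on its three readings being consecutive, and on draws keeping to the 5-minute schedule around 180 minutes. The doses in units also rest on the assumed correction factors. If the single value in VI.c were the rule, no bolus would be due at 50-59 and the point would fall away.

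**What to change.** Amend V.d.ii as follows.
- State that the hypoglycemia threshold is PG below 60 mg/dl on three consecutive 5-minute measurements, or below 50 mg/dl once. The word consecutive matters: without it, M-H-M could be counted as two readings towards the three.
- If the latest PG at 3 hours is below 60 mg/dl and the threshold is not yet met, hold the second bolus while 5-minute readings continue.
- If the threshold is then met, give no second bolus.
- If a reading of 60 mg/dl or above comes first, give the bolus then, dosed on that reading, and run the two hours from it.
- If a draw is missed, the supervising clinician decides.

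The rule for a subject at 60 or above at 180 minutes, and the carbohydrate tiers, stay as they are.

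The cost is a small change to a dosing rule, so it is more than an editorial correction. On schedule the bolus is delayed by at most 10 minutes. On release the dose is at least 20/CF units instead of 10/CF to 19/CF. Sample size and analysis are unaffected.
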